1.3. International Studies of HIV Incidence in Pregnancy and Postpartum

In a meta-analysis, using data from 19 international cohorts, Drake et al concluded that the pooled HIV incidence rate during pregnancy/postpartum was 3.8/100 PWY (95% CI 3.0-4.6): 4.7/100 PWY during pregnancy and 2.9/100 PWY postpartum (p=0.18) [9] (Fig 3). When compared to earlier studies, current programmatic data reflects a shift in the new HIV infection epidemic (Figures 2 and 3). The higher HIV incidence in women postpartum is hypothetically due to a longer exposure/observational period (12 – 18 months) compared to exposure during the antepartum period (maximum 6-8 months). Other plausible reasons for the higher HIV incidence postpartum include possible behavioural changes and changes in relationship dynamics over a 12-18 month period. These risk factors are yet to be confirmed in prospective studies.

Figure 3. A forest-plot of HIV incidence in pregnancy and postpartum as per a metaanalysis of international studies by Drake et al, 2014 [9].

HIV incidence was significantly higher in African than non-African countries (3.6% versus 0.3%, respectively; p<0.001) and more importantly the meta-analysis revealed that risk of HIV in non-pregnant/non-postpartum women was not significantly different from the pregnant (HR 1.3, 95% CI 0.5-2.1) or postpartum women (HR 1.1, 95% CI 0.6-1.6). These findings support our rationale for pregnant and postpartum women to be regarded at similarly high risk as their non-pregnant counterparts. However, the impact of newly acquired maternal HIV infections on the unborn/lactating infant has far more outreaching consequences and for this reason these young pregnant women or lactating women need to be prioritized for access to PrEP.

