3.1 Population at Risk

Pregnant women seek antenatal care at any of the 17 primary health care clinics and deliver at the Prince Mshiyeni Memorial District hospital. Women range in age between 16 and 40 years, and almost half (46%) of the women who deliver at the hospital are adolescents are young women (<25 years). Approximately 25% are primigravid and the average gestational age at first visit is 28 weeks, although 48% register prior to 20 weeks of gestation. The PHC clinics have an active PMTCT program. As prescribed in the National HIV treatment guidelines, pregnant women are offered HIV counselling and testing at their first antenatal visit. A serial HIV testing algorithm using Point of Care serological tests is implemented at all public health facilities. Women who are positive on the first POC test are immediately confirmed infected if the second POC test is also reactive. If pregnant women test negative on the first POC, they receive risk reduction counselling and informed of an opportunity to repeat the test 3 monthly during pregnancy and post-delivery.

In a maternity audit conducted at the District Hospital (PMMH) during a 3 month period in 2011 and 2014, 1732 (37.3%) and 2219 (38.7%) women were HIV positive among the 4644 and 5738 deliveries respectively. A third (34%) of the HIV infected pregnant women were <25 years and 52% of women who remained HIV negative by the time of delivery were between 18 and 24 years old.

In a cohort study conducted at a PHC clinic in Umlazi, 38% (548/1446) of antenatal attendees tested HIV positive and almost half (47%) of these women were <25 years

of age. The prevalence of Trichomonas, Chlamydia and Neisseria in pregnant women was 15.6%, 17.7% and 6.4% respectively. All three STIs were significantly more common in younger women <25yrs (17.2%, 21% and 8.6% vs 12.4%, 13.2% and 3.4% respectively) than older women. Among 636 pregnant women tested for HSV-2 shedding in cervical secretions, 52 (8.18%; 95%CI 6.22-10.65) women tested positive by DNA PCR. HSV-2 shedding was detected in 10.4% of HIV positive women and 6.7% of HIV negative women.

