Based on current data (maternal adverse events, maternal and infant bone mineral content depletion), all other adverse birth outcomes and maternal and infant adverse events can be housed within this sample size and will have smaller D as the relative prevalence decreases toward 0 i.e. narrower equivalence zones. Assuming a loss to follow-up of 5%, we would need 442 women in each group (884 in both arms combined) for the two year time frame of the study.

Outcome	n/N	Prevalence	Required sample size in each group for proposed equivalence trial	Total required sample size for proposed equivalence trial
Pre-term	1096/5916	18.5%	421	842
LBW	651/5916	11.0%	274	548
Small for GA	429/5916	7.3%	189	378
VLBW	141/5916	2.4%	64	128
Stillbirth	130/5916	2.2%	58	116

Main endpoint 1: sample size for safety in pregnancy for birth outcomes Prevalence adverse birth outcomes among HIV-ve (in descending order)

Based on a non-inferiority trial design: A sample size of 421 in the treatment group and 421 in the control group (i.e. 842 in total) achieves 80% power to detect a non-inferiority margin difference between the group proportions of 0.075 or 7.5%. The reference group proportion (pre-term delivery birth outcome) is 0.185 or 18.5%. The treatment group proportion is assumed to be 0.26 or 26% under the null hypothesis of inferiority. The power was computed for the case when the actual treatment group proportion is 0.185 or 18.5%. The test statistic used is the two-sided Z test (unpooled). The significance level of the test was targeted at two-sided 0.05 or 5%.

Secondary Endpoint

PASS 12 sample size software (Hintze, J. (2013). PASS 12. NCSS, LLC. Kaysville, Utah, USA. www.ncss.com) was to calculate this sample size. In order to show a 50% reduction in HIV infections, with significance level of 0.05 or 5% and 80% power, we would need to observe 66 HIV infections in total (44 in control arm [cumulative incidence of 12.72%] and 22 in the intervention arm [cumulative incidence of 6.36%]). This assumes an HIV incidence of 3 per 100 person years during the 6 months of pregnancy and 6 per 100 person years during the 18 months of breastfeeding [9]. Based on these assumptions, we would require 334 subjects in group or 668 in total. Assuming a loss to follow-up of 10%, we would need to increase this to 346 women in each group (692 in both arms combined) for the two year time frame of the study.

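### Section 10.3 sizes the HIV endpoint on 3 and 6 per 100 person-years and cites [9], which the protocol reports as 4.7 and 2.9; on those rates power is 57–63% (z test) at 421–442 per arm, not 80%.

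*Combined protocol and SAP*

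**What the plan says.** Section 10.3, under Secondary Endpoint, aims to detect a halving of HIV infections and sets the requirement: "with significance level of 0.05 or 5% and 80% power, we would need to observe 66 HIV infections in total". The split between the arms is given as "44 in control arm [cumulative incidence of 12.72%] and 22 in the intervention arm [cumulative incidence of 6.36" (the last figure also a percentage). The rates behind these figures are stated next: "This assumes an HIV incidence of 3 per 100 person years during the 6 months of pregnancy and 6 per 100 person years". The second rate is applied to an 18-month breastfeeding period, and the sentence is referenced to [9]. The calculation concludes that "we would require 334 subjects in group or 668 in total", raised to 346 per group for 10% loss.

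Section 1.3 reports the same reference as "4.7/100 PWY during pregnancy and 2.9/100 PWY postpartum (p=0.18) [9". The synopsis repeats the two rates, and the reference list confirms that [9] is that meta-analysis.

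The trial itself is sized on preterm delivery: 421 per arm, or 442 with 5% loss. Section 10.4 plans Fisher's exact test for incident HIV infections, and 95% confidence intervals for the cumulative incidence in each arm.

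**The concern.** The cited source, as the protocol reports it, has the higher rate in pregnancy. The sizing has the higher rate in breastfeeding, at about twice the reported postpartum figure (6 / 2.9 = 2.1). Breastfeeding accounts for 1.5 of the 2 assumed years, so this rate drives the expected number of infections.

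A reader of section 10.3 will believe that the trial has 80% power to show a halving of HIV infections. If incidence is nearer to the reported [9] rates, a true halving would be missed in roughly four or more of ten such trials at the full planned size. A non-significant result could then be misread as evidence of no benefit.

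**Working it through.** **Inputs.** Two-sided 5% level (the HIV paragraph does not state sidedness, but two-sided reproduces its figure), 80% power, 50% reduction, equal allocation, 0.5 years of pregnancy and 1.5 years of breastfeeding (section 10.3). Rates from [9] as reported in section 1.3. Arm sizes 334, 421 and 442 (section 10.3). Fisher's test (section 10.4).

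**Step 1: reproduce the plan's figures.** Two proportions, 12.72% v 6.36%, pooled variance, no continuity correction: n = 334 per arm, power 80.0%. The event count follows from Schoenfeld's formula: 4 × (1.96 + 0.8416)² / (ln 0.5)² = 65.3, rounded up to 66. The 12.72% equals 44/346. Fisher's test on the same risks at 334 per arm has 77% power, so the stated 80% is a z-test figure.

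**Step 2: do 3 and 6 give 12.72%?** Cumulative hazard = 0.03 × 0.5 + 0.06 × 1.5 = 0.105. Control risk is 10.5% if taken linearly, or 1 − exp(−0.105) = 9.97%. Neither is 12.72%.

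**Step 3: the rates reported from [9].** Cumulative hazard = 0.047 × 0.5 + 0.029 × 1.5 = 0.0235 + 0.0435 = 0.067. Control risk is 6.70% (linear) or 1 − exp(−0.067) = 6.48%. Halving the rate gives 3.35% or 3.29% in the intervention arm.

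**Step 4: infections and power.** Infections = n × (control risk + intervention risk). Each range runs from the exponential to the linear form. Fisher power is by exact enumeration. Loss to follow-up is not deducted.

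| Rates per 100 PY | n per arm | Infections | Power, z | Power, Fisher |
|---|---|---|---|---|
| 3 and 6 | 334 | 50–53 | 66–71% | 61–67% |
| 3 and 6 | 421 | 64–66 | 76–81% | 73–78% |
| 3 and 6 | 442 | 67–70 | 78–83% | 75–80% |
| 4.7 and 2.9 | 334 | 33–34 | 48–51% | 41–44% |
| 4.7 and 2.9 | 421 | 41–42 | 57–61% | 52–55% |
| 4.7 and 2.9 | 442 | 43–44 | 59–63% | 54–58% |

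At 398 per arm (442 less 10%), the [9] rates give 39–40 infections and 55–58% power (z) or 49–53% (Fisher). About 667–718 per arm would be needed for 80% power by the z test.

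**Step 5: could local data support 3 and 6?** Section 1.2 reports 1.8% antenatal seroconversion in the province, and postnatal seroconversion of 5% overall and 6.2% in the trial's district. These are percentages, not rates. As an assumption, take the exposure windows named in section 1.3 (6–8 months antenatal at most, 12–18 months postnatal) as the retest intervals, with rate = −ln(1 − p) / years:
- 1.8%: 0.0182 / 0.667 to 0.0182 / 0.5 = 2.7–3.6 per 100 PY.
- 5%: 0.0513 / 1.5 to 0.0513 / 1 = 3.4–5.1 per 100 PY.
- 6.2%: 0.0640 / 1.5 to 0.0640 / 1 = 4.3–6.4 per 100 PY.

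The antenatal 3 falls inside its range. The postnatal 6 is reached only with the district figure and an interval close to 12 months.

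**The case against.** The strongest reply is that only the reference number is wrong. Section 1.2 reports postnatal seroconversion at 2 to 6 times the antenatal level, and section 1.3 says that recent programme data show a shift from earlier studies. The trial enrols women aged 18–24 selected as high risk in one district, whereas [9] pools 19 international cohorts. If 3 and 6 are right, the trial's 421–442 per arm gives 64–70 infections and 76–83% power by the z test, close to what is claimed. This stands as a live alternative, and it is why the documents cannot settle which rates are correct. It does not remove the mismatch: section 10.3 cites [9], shows no conversion from percentages, and its postnatal rate lies near the top of what the local figures allow.

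A reader might infer that the trial will see only half the required infections and has 41–48% power. That holds only at 334 per arm, which is not the trial's size, and the lower end sets a Fisher figure against a z-test claim. Nor can the whole fall from 80% at 334 be charged to the citation, since 3 and 6 already give only 66–71% there.

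A reader might also infer that six months of antenatal follow-up is untenable, because section 3.1 says "the average gestational age at first visit is 28 weeks", leaving about 12 weeks to term. The same sentence says that 48% register before 20 weeks, and the figure describes all clinic attendees. The design scheme starts at 14 weeks or later and Appendix 5 places enrolment at 14 weeks; 14 to 40 weeks is 26 weeks, or six months. Twelve weeks is at most a sensitivity value.

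Finally, HIV is a secondary endpoint that does not set the sample size, the objective is worded as estimating incidence, and per-arm intervals are already planned. That limits the consequence, but section 10.4 also plans a formal between-arm test.

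**Conclusion.** The concern holds in this form. Section 10.3 rests its 80% power on rates that its cited source, as the protocol reports it, does not give. On the reported rates the planned 421–442 per arm yields 41–44 of the 66 infections (62–67%) and 57–63% power by the z test, or 52–58% by the planned Fisher test. A second, separate inconsistency is that the stated 3 and 6 give a control risk of 10.0–10.5%, not 12.72%.

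These figures assume constant rates within each period, 0.5 and 1.5 years at risk for every woman, a true halving of the rate, and no loss to follow-up. The size of the shortfall depends on the [9] rates applying to this population. If the local data are the true source and support 3 and 6, most of the shortfall at the planned size disappears and the defect is the citation together with the unexplained 12.72%. It should be corrected, but it does not threaten the trial's main safety comparison.

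**What to change.** In section 10.3:
- Either use the rates that the protocol reports from [9], or cite the local programme data as the source of 3 and 6. In the second case, show the conversion from percent seroconverting to a rate, with the retest interval stated.
- Reconcile the chosen rates with the 12.72% and 6.36%, or replace those figures.
- Restate expected infections and power at 421–442 per arm, for Fisher's test, over the plausible range of rates. A shorter antenatal period may be added as a sensitivity value.

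In section 10.4, add an estimated between-arm effect with its 95% CI (per-arm intervals alone do not supply this), and say that the HIV comparison will be interpreted through it.

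The cost is rewording and recalculation, with no added participants or procedures. The stated power becomes less favourable.

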10.4 Analysis Plan

Full details of the proposed analyses will be described in a statistical analysis plan that will be developed once enrollment to the study begins and prior to the commencement of analyses. Hence, here we limit the description of the proposed analyses to those for the primary safety endpoint.

Analyses will use the principle of intention-to-treat (i.e., using the randomised treatment assignment, whether or not study drugs were actually taken) and will include all randomised participants. This is generally the more conservative approach for analysis of trial data. However, it has been proposed that the smaller differences commonly observed in intention-to-treat analysis have the opposite effect when testing equivalence or non-inferiority. Hence for sensitivity analysis purposes (and as a required by the FDA) we will also perform a per protocol data analysis for comparative purposes (Walker, E., & Nowacki, A. S. (2011). Understanding Equivalence and Noninferiority Testing. Journal of General Internal Medicine, 26(2), 192–196. http://doi.org/10.1007/s11606-010-1513-8).

HIV Prevention Pregnancy Post-delivery Version 1.0

Data will be processed and analyzed using Stata 13.0 (tataCorp. 2013. Stata Statistical Software: Release 13. College Station, TX: StataCorp LP.) and R 3.2.4 (R Core Team (2016). R: A language and environment for statistical computing. R

Foundation for Statistical Computing, Vienna, Austria. ISBN 3-900051-07-0, URL http://www.R-project.org/.).

The primary objective is to compare the frequency and seriousness of adverse events in women receiving tenofovir/emtricitabine in pregnancy and their newborn as opposed to women not receiving tenofovir/emtricitabine during pregnancy and their newborn. The number of adverse events experienced during pregnancy and post-delivery will be summarized for each of the study arms. This will also be stratified by seriousness of the adverse event. The number of adverse events will be compared between the study arms using Fisher's Exact test. Furthermore we will use the most widely used approach to test equivalence, namely the two one-sided test (TOST) procedure (Schuirmann DJ. A comparison of the two one-sided tests procedure and the power approach for assessing equivalence of average bioavailability. J Pharmacokin Biopharm. 1987;15:657–680. doi: 10.1007/BF01068419). Furthermore we will also employ a hierarchical or random effects modeling approach for a non-inferiority analysis for the primary endpoints.

A secondary objective is to compare the number of incident HIV infections in women during pregnancy alone and thereafter during breastfeeding. The analysis will be stratified by levels of PrEP adherence, partner involvement, condom usage and relationship dynamics. The cumulative incidence and associated 95% confidence intervals will be calculated for each study arm. The number of incident events will be compared for statistical difference between the study arms using Fisher's Exact test.

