To explore the safety of Truvada when used as PrEP in combination with current recommendations for prevention of sexually transmitted infections and HIV in young women at substantial risk of HIV acquisition during pregnancy and lactation.

2.2 Primary Objective:

 To compare the frequency and seriousness of specific adverse events related to TDF/FTC in women and their children in Arm A (exposure to TDF/FTC) and Arm B (no exposure to TDF/FTC) during pregnancy until breastfeeding cessation.

2.3 Secondary Objectives:

- To estimate HIV incidence in women in ARM A with ARM B at delivery and at 18 months post-delivery.
- To determine the interdependency of adherence to a once daily oral TDF/FTC regimen and standard HIV prevention methods during pregnancy and postdelivery.
- To measure antiretroviral drug (TDF/FTC) level in women and their infants in association with adherence, safety and level of protection (plasma and breastmilk)
- To detect drug resistance among women who acquire HIV infection and correlate the treatment outcomes (after initiating immediate ARV treatment) with drug resistance
- To determine mother-to-child transmission of HIV among women who acquire incident infections during pregnancy and breastfeeding and the frequency of drug resistance in their infected babies

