7.12 At Follow-up Visits during Product Use

At follow-up visits antenatal week 4 through week 74, study staff will:

- Update contact information (when necessary);
- Conduct pill count of product returned by participant, and document any product returned to participant;
- Collect information on adherence to the daily pill-taking regimen;
- Conduct risk reduction counseling, including pre- and post-test HIV counseling and distribute condoms;
- Conduct study product adherence counseling;
- Conduct contraceptive counseling as appropriate, re-supply contraceptive method as needed;

- Collect blood by venepuncture (10ml) and:
 - Perform HIV rapid antibody testing according to the algorithm described at the enrollment visit.
 - ✓ Test for ALT, AST, creatinine and phosphorus. If results are abnormal, repeat regularly until resolution to ≤ Grade 1 or until stabilization. Any required followup will be done per local standard of care.
 - ✓ Store plasma and ULPC aliquots for HIV PCR testing, QA and confirmatory laboratory testing as needed. Also store one plasma aliquot (if sufficient sample available) and one serum aliquot for potential future HIV related research;
 - ✓ Screen and treat other STIs using the syndromic management approach
 - Collect cervical/vaginal swabs for storage and subsequent screening for STIs using molecular techniques.
- Conduct adverse event assessment as per the US Division of AIDS Adverse Event Reporting and Toxicity Grading;
- Conduct physical and/or pelvic examination if clinically indicated; and
- Record medications taken since last visit.
- Complete the Final Status CRF if the participant does not require further follow-up due to risk of Hepatitis B flare and/or HIV seroconversion.

Participants will be allowed to complete each follow-up visit up to five days prior to and two (for the week 4 follow-up visit) or four (for later follow-up visits) days after their next 4-week (28 days) target visit date. If participants complete a visit outside the given window for that specific visit, the visit will be regarded an interim visit and an appointment for the next scheduled visit will be given.

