8.5 Definitions

Adverse Event:

An adverse event (AE) is defined as any untoward medical occurrence in a clinical research participant administered an investigational product and which may or may not have a causal relationship with the investigational product. As such, an AE can be an unfavorable or unintended sign (including an abnormal laboratory finding, for example), symptom or disease temporally associated with the use of an investigational product, whether or not considered related to the product. Study participants will be instructed to contact the study clinician to report any AEs their infants may experience.

Serious Adverse Event:

A serious adverse event (SAE) is any untoward medical occurrence that at any dose that results in death, is life threatening, requires inpatient hospitalization or prolongation of existing hospitalization, results in persistent or significant disability/incapacity, or is a

congenital anomaly/birth defect (April 1996 International Conference on Harmonisation (ICH), Good Clinical Practice: Consolidated Guidance, (ICH E6). Important medical events that may not be immediately life – threatening or result in death or hospitalization but may jeopardize the patient or may require intervention to prevent one of the outcomes listed in the definition above may also be considered to be serious. (October 1994 ICH guidance (E2A), Clinical Safety Data Management: Definitions and Standards for Expedited Reporting).

SUSAR: Suspected, Unexpected Serious Adverse Reaction:

Serious (see SAE definition above)

Related (i.e. there is a reasonable possibility that the AE may be related to the study agent)

Unexpected (see definition below)

Unexpected AE:

An AE, the nature or severity (intensity) of which is not consistent with the applicable agent information (Investigator's Brochure, package insert, or summary of agent characteristics).

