10.3 Sample Size Calculation

In view of the limited evidence of safety data from studies of PrEP (TDF/FTC) use in pregnancy, we based our sample size on data provided in studies of ART treatment in HIV infected pregnant women. In few studies, comparisons were made to HIV uninfected pregnant women.

To compare the frequency and seriousness of adverse events in women receiving tenofovir/emtricitabine in pregnancy as opposed to women not receiving tenofovir/emtricitabine in pregnancy, we have based our sample size on the main clinically relevant pregnancy outcome.

Adverse Pregnancy Outcomes

Although all pregnancy outcomes will be compared between the intervention (immediate PrEP) and control (deferred PrEP) groups, we based our sample size on the expected preterm delivery proportion among HIV uninfected women (South Africa 18.5%, Botswana 19%). A sample size of 421 in the Immediate PrEP group and 421 in the Deferred PrEP group (i.e. 842 in total) achieves 80% power to detect a non-inferiority margin difference between the group proportions of 0.075 or 7.5%. The reference group proportion (deferred PrEP) of pre-term delivery pregnancy outcome as a main clinically-relevant adverse event is 0.185 or 18.5%.

Maternal Adverse Events (2% margin difference)

Other maternal adverse events will include abnormal chemistry (Grade \geq 2) results. As reported in the PROMISE study, Grade 2 or higher chemistry abnormalities were significantly higher in HIV infected pregnant women randomized to TDF containing ART (3%) compared to AZT/sdNVP (1%) (p<0.03).

Maternal and Infant Bone Mineral Density (4-7% margin difference)

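### Section 10.4 compares adverse event counts split only by seriousness and does not carry forward the Grade 2 or higher chemistry threshold of 10.3

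*Combined protocol and SAP*

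**What the plan says.** Section 10.4 sets out the adverse event analysis in three steps. First, "The number of adverse events experienced during pregnancy and post-delivery will be summarized for each of the study arms". Then, "This will also be stratified by seriousness of the adverse event". Finally, "The number of adverse events will be compared between the study arms using Fisher's Exact test". It adds two one-sided tests and a "hierarchical or random effects modeling approach for a non-inferiority analysis for the primary endpoints". No severity grade appears anywhere in 10.4.

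Other sections bear on what is counted:

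- Section 2.2 gives the primary objective: "To compare the frequency and seriousness of specific adverse events related to TDF/FTC in women and their children". When 10.4 restates the objective, it omits the restriction to specific, drug-related events.
- Section 8.5 defines an adverse event broadly: "an AE can be an unfavorable or unintended sign (including an abnormal laboratory finding, for example". It sets no grade floor. Its definition of a serious event is the ICH one: death, threat to life, admission, disability, congenital anomaly or an important medical event.
- Section 10.3, under maternal adverse events, names abnormal chemistry at Grade 2 or above. It cites an earlier trial in which "Grade 2 or higher chemistry abnormalities were significantly higher in HIV infected pregnant women" given TDF-containing treatment, at 3% against 1%.
- Section 7.12 has staff grade events at follow-up visits: "Conduct adverse event assessment as per the US Division of AIDS Adverse Event Reporting and Toxicity Grading".
- Section 10.2 lists creatinine clearance, pregnancy outcomes and bone mineral density as main outcomes. ALT, AST and phosphorus are measured (7.12, 7.21, Appendix 5) but are not listed there.

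**The concern.** Seriousness and severity are different scales. A woman with a Grade 2 or 3 rise in ALT who is not admitted would usually be classed as non-serious. Followed as written, 10.4 puts her with women who had a minor complaint or a trivial laboratory change. Neither the all-event comparison nor either seriousness stratum isolates the abnormality that 10.3 singles out.

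For creatinine this matters less, because renal function is a main outcome in its own right. For ALT, AST and phosphorus, the adverse event comparison is the only formal between-arm analysis the document describes. In a trial whose aim is safety in pregnancy and lactation, a comparison diluted towards no difference could be read as reassurance that it cannot give.

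**Working it through.** **Inputs from the documents.** 421 women per arm, or 442 after the allowance for loss; two-sided 5% level; Fisher's exact test; Grade 2+ chemistry 3% versus 1% (10.3, 10.4).

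**Inputs assumed.** One yes/no record per woman, because 10.4 does not say how counts of events enter a Fisher table. A proportion q of women in each arm has some other event that would be pooled, unaffected by the drug and independent of the chemistry abnormality. The documents give no overall adverse event rate, so q is varied.

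**Step 1. Reproduce the plan's sample size.** Non-inferiority, 18.5% in both arms, margin 7.5 points, unpooled variance:

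n = 2 × 0.185 × 0.815 × (1.960 + 0.842)² / 0.075² = 420.8, so 421 per arm.

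The stated 421 is confirmed. It was set for preterm delivery, not for chemistry abnormalities.

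**Step 2. Grade 2+ chemistry on its own.** Exact two-sided Fisher power for 3% versus 1% is 47% at 421 per arm and 49% at 442. By the usual normal-approximation formula, 80% power would need 769 per arm (866 with continuity correction).

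**Step 3. Pool it with other events.** The proportion of women with any event becomes 1 − (1 − q)(1 − g), where g is 0.03 or 0.01.

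| q (assumed) | TDF/FTC arm | Control arm | Difference (points) | Fisher power, 421 per arm |
|---|---|---|---|---|
| 0 (chemistry alone) | 3.0% | 1.0% | 2.0 | 47% |
| 5% | 7.85% | 5.95% | 1.9 | 16% |
| 10% | 12.7% | 10.9% | 1.8 | 11% |
| 30% | 32.1% | 30.7% | 1.4 | 6% |

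Example for q = 5%: 1 − 0.95 × 0.97 = 0.0785 and 1 − 0.95 × 0.99 = 0.0595.

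The difference shrinks only slightly. Most of the loss comes from variance. The approximate standard error of the difference is √(0.03 × 0.97/421 + 0.01 × 0.99/421) = 0.0096 for chemistry alone, and √(0.321 × 0.679/421 + 0.307 × 0.693/421) = 0.032 at q = 30%. The corresponding 95% half-widths (1.96 × SE) are 1.9 and 6.3 percentage points.

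**Step 4. Would an endpoint of any Grade 2+ event be enough?** No. The same formula applies, with q now the proportion of women having some other Grade 2+ event. If that is 5% or 10%, power is again 16% or 11%. The comparison has to be restricted to chemistry.

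**The case against.** There is a fair case that the defect is one of wording.

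- **Grade 1 laboratory changes may not be meant to count.** A reader might infer that the plan counts laboratory changes of every grade. That is an inference from silence in 10.4 combined with the broad definition in 8.5. Other text points the other way: 10.3 names chemistry at Grade 2 or above, 7.12 treats a return to Grade 1 as resolution, and 2.2 limits the objective to specific drug-related events. This stands. The supportable point is that 10.4 does not carry these limits forward.
- **Much of the anticipated toxicity has its own outcome.** A reader might infer that TDF toxicity could not be detected at all. The documents do not support that, since 10.2 lists renal function, pregnancy outcomes and bone density separately. The gap is ALT, AST and phosphorus.
- **Section 10.3 does not predict a 3% versus 1% difference here.** It cites that result from HIV-infected women on treatment, while its own sample size assumes zero difference. The figures serve only as the plan's own reference case.
- **The background rate is unknown.** This is true, but 5% of women with another event is already enough to cut power from 47% to 16%.
- **A later SAP will give details.** Section 10.4 defers full details but says that it describes the primary safety endpoint analyses, so the definition belongs there. The trial is open label and that SAP is to be developed after enrolment begins, which makes a grade threshold fixed now easier to defend.
- **The separated comparison is itself underpowered.** This stands and must be stated in the plan.

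**Conclusion.** The point holds as a specification gap that is cheap to close. Section 10.4 neither applies the Grade 2+ chemistry threshold of 10.3 nor uses the grades collected under 7.12, and seriousness cannot stand in for grade. Applied literally, it reduces power for the cited 3% versus 1% from about 47% to between 16% and 6% when 5% to 30% of women have another event. Those figures rest on one record per woman, independence of the other events from drug and chemistry, and background rates that are assumed.

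Separating the chemistry endpoint does not make the trial adequately powered for it. It gives a legible estimate with a half-width of about 2 percentage points, in place of one mixed with unrelated events.

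**What to change.** In 10.4, add a separate between-arm comparison of the proportion of women with at least one post-randomisation Grade 2 or higher chemistry abnormality (ALT, AST, creatinine or phosphorus), reported as a risk difference with a 95% confidence interval. Do the same for infant serum creatinine. For infants, name the grading table, and confirm that control infants are sampled: 7.13 and Appendix 6 imply that they are, whereas 7.21 mentions only exposed infants.

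State beside the analysis that power for 3% versus 1% is about 47% at 421 per arm, so a non-significant result is not evidence of safety. Keep the all-event and seriousness tables as descriptive support. Leave the definition in 8.5 unchanged, because narrowing it would reduce safety capture without helping the analysis.

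The cost is a few sentences and one more table. Maternal grades and the laboratory values are already planned. The downside is one more formal comparison, with limited power.
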